Dose Modifications – Phase 1 dose escalation (ALRN-6924 administered as single agent therapy)

In the event a Grade 4 AE considered related to ALRN-6924 is observed, the patient must be discontinued from the study. Exceptions include Grade 4 neutropenia lasting <3 days, and emesis, diarrhea or electrolyte abnormalities that resolve within 2 days on optimum treatment. For these exceptions, treatment may be delayed for up to 2 weeks to allow resolution of the toxicity (i.e., return to Grade ≤ 1 or baseline), followed by re-treatment at a reduced dose. Two dose reductions are permitted, a third dose reduction will require evidence of clinical benefit and approval by the Medical Monitor. Relevant labs should be repeated as medically indicated.

In the event a Grade 3 AE considered related to ALRN-6924 is observed (exceptions are Grade 3 fatigue, nausea, emesis, diarrhea or clinically insignificant electrolyte abnormalities that resolve within 2 days on optimum treatment), treatment may be delayed for up to 2 weeks to allow resolution of the toxicity, followed by re-treatment at a reduced dose. Two dose reductions are permitted, a third dose reduction will require evidence of clinical benefit and approval by the Medical Monitor. Relevant labs should be repeated as medically indicated.

Following related Grade 3 and Grade 4 AEs (as permitted), the dose for re-treatment will be reduced by 25% intervals (e.g., if the dose is 3.1 mg/kg, the dose will be reduced sequentially to 2.3 mg/kg and 1.7 mg/kg).

For other clinically significant AEs, treatment may be delayed by up to 2 weeks to allow for the resolution of AEs to an acceptable level, and a dose reduction may be made as described above at the discretion of the Investigator in consultation with Sponsor's Medical Monitor. If a patient experiences multiple AEs, decisions on dosing delay or dose reduction will be based on the most severe AE. Any patient who experiences recurrent, clinically significant AEs after one dose reduction may undergo one additional dose reduction. Patients who continue to experience clinically significant AEs after a 2-week delay or the maximum allowed number of dose reductions will be discontinued from study treatment.

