5.8 Dose and Schedule Adjustments for Toxicity

5.8.1 Dose Modifications – Phase 1 dose escalation (ALRN-6924 administered as single agent therapy)

In the event a Grade 4 AE considered related to ALRN-6924 is observed, the patient must be discontinued from study treatment. Exceptions include Grade 4 neutropenia lasting <3 days, and emesis, diarrhea or electrolyte abnormalities that resolve within 2 days on optimum treatment. For these exceptions, treatment may be delayed for up to 2 weeks to allow resolution of the toxicity (i.e., return to Grade ≤ 1 or baseline), followed by re-treatment at a reduced dose. Two dose reductions are permitted; a third dose reduction will require evidence of clinical benefit and approval by the Medical Monitor. Relevant labs should be repeated as medically indicated.

In the event a Grade 3 AE considered related to ALRN-6924 is observed (exceptions are Grade 3 fatigue, nausea, emesis, diarrhea or clinically insignificant electrolyte abnormalities that resolve within 2 days on optimum treatment), treatment may be delayed for up to 2 weeks to allow resolution of the toxicity, followed by re-treatment at a reduced dose. Two dose reductions are permitted, a third dose reduction will require evidence of clinical benefit and approval by the Medical Monitor. Relevant labs should be repeated as medically indicated.

Dose modifications for re-treatment following related Grade 3 and Grade 4 AEs (as permitted): patients will be re-treated at the preceding dose level (per Figure 9).

For other clinically significant AEs, treatment may be delayed by up to 2 weeks to allow for the resolution of AEs to an acceptable level, and may continue treatment at a reduced dose level as described above at the discretion of the Investigator in consultation with Sponsor's Medical Monitor. If a patient experiences multiple AEs, decisions on dosing delay or dose reduction will be based on the most severe AE. Any patient who experiences recurrent, clinically significant AE after one dose reduction may undergo one additional dose reduction. Patients who continue to experience clinically significant AEs after a 2-week delay or the maximum allowed number of dose reductions will be discontinued from the study.

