Adverse events considered for dose reduction should not include the events assessed by the Investigator as exclusively related to underlying disease or other medical condition or concomitant treatment. A patient who experiences an AE considered related to ALRN-6924 that does not meet the requirement for discontinuation may continue on study if the patient is receiving clinical benefit and/or the Investigator feels continued participation is in the best interest of the patient. In such cases, at the Investigator's discretion and in agreement with Sponsor's Medical Monitor, the dose for a patient may be reduced as described above.

A patient who experiences a DLT must continue treatment at a reduced dose level, or discontinue ALRN-6924 treatment (if Grade 4 related AE), as described above at the discretion of the Investigator and in agreement with Sponsor's Medical Monitor until disease progression or unacceptable toxicity. Once the dose has been reduced for a patient, it may not be re-escalated.

5.8.2 Dose Modifications – Phase 2a dose expansions in PTCL (ALRN-6924 administered as single agent therapy)

In the event a non-hematologic Grade 4 AE considered related to ALRN-6924 is observed, the patient must be discontinued from the study. Exceptions include emesis, diarrhea or electrolyte abnormalities that resolve within 2 days on optimum treatment. For these exceptions, treatment may be delayed for up to 2 weeks to allow resolution of the toxicity (i.e., return to Grade ≤ 1 or baseline), followed by re-treatment at a reduced dose. Relevant labs should be repeated as medically indicated.

In the event a non-hematologic Grade 3 AE considered related to ALRN-6924 is observed (exceptions are Grade 3 fatigue, nausea, emesis, diarrhea or clinically insignificant electrolyte abnormalities that resolve within 2 days on optimum treatment), treatment may be delayed for up to 2 weeks to allow resolution of the toxicity, followed by re-treatment at a reduced dose. Relevant labs should be repeated as medically indicated.

For hematologic toxicities, patients must discontinue treatment with ALRN-6924 if

- Neutrophil counts $< 0.5 \times 10^9/L$ for > 5 days, or
- Platelet counts $< 10 \times 10^9/L$, or
- Hemoglobin $< 6\text{g/dL}$ (despite RBC transfusion or Erythropoiesis-Stimulating Agent (ESA) administration)

Patients must interrupt treatment if

- Neutrophil counts $< 0.5 \times 10^9/L$ for ≤ 5 days, or

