- Platelet counts $< 25 \times 10^9/L$ and $> 10 \times 10^9/L$, or
- Hemoglobin $< 8\text{ g/dL}$ and $> 6\text{ g/dL}$

After resolution of hematologic toxicity (i.e., return to Grade ≤ 1 or baseline), patients may continue at a reduced dose. Relevant labs should be repeated as medically indicated.

Following related Grade 3 and Grade 4 AEs (as permitted), the dose for re-treatment will be reduced by 25% intervals (e.g., if the dose is 3.1 mg/kg, the dose will be reduced sequentially to 2.3 mg/kg and 1.7 mg/kg). Two dose reductions are permitted, a third dose reduction will require evidence of clinical benefit and approval by the Medical Monitor.

5.8.3 Dose Modifications – Phase 2a Dose Expansion in MDM2 Amplified or MDM2/CDK4 Co-amplified Solid Tumors (ALRN-6924 plus palbociclib)

Dose modifications of ALRN-6924 will be as described in Section 5.8.1. Dose modifications of palbociclib should be made in accordance with the current approved US prescribing information.

In the event that palbociclib administration must be discontinued, the patient may continue to receive ALRN-6924 as a study participant until one of the criteria for treatment discontinuation has been met. However, if discontinuation of ALRN-6924 is required, patients will be considered to have discontinued study treatment. Those patients may continue to receive palbociclib treatment at the Investigator's discretion.

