6.13 End of Treatment and End of Study

Approximately 30 days (+/- 5 days) after the last dose of study drug, an end of treatment visit will be conducted. For patients in Phase 1, this visit will be the same as the end of study. Patients in Phase 2 will remain on study and be followed for survival and subsequent therapies.

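### Section 5.8.2 takes PTCL expansion patients with a related non-hematologic Grade 4 event off the study, while 6.13 keeps them on for survival follow-up; the rules inherited by the combination cohort also conflict

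*Protocol*

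**What the plan says.** **PTCL expansion.** Section 5.8.2 reads: "In the event a non-hematologic Grade 4 AE considered related to ALRN-6924 is observed, the patient must be discontinued from the study". The synopsis has the same sentence. The rule is limited: "Exceptions include emesis, diarrhea or electrolyte abnormalities that resolve within 2 days on optimum treatment". Blood-count toxicity is worded differently within the same section: "For hematologic toxicities, patients must discontinue treatment with ALRN-6924 if" certain thresholds are crossed.

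**Combination cohort.** Section 5.8.3 refers back to the Phase 1 rules: "Dose modifications of ALRN-6924 will be as described in Section 5.8.1". The synopsis makes the same cross-reference. Those Phase 1 rules exist in two versions:
- For a related Grade 4 event the synopsis says "In the event a Grade 4 AE considered related to ALRN-6924 is observed, the patient must be discontinued from the study", while Section 5.8.1 says "In the event a Grade 4 AE considered related to ALRN-6924 is observed, the patient must be discontinued from study treatment".
- For events that persist after a delay or after all permitted reductions, 5.8.1 says that patients who reach "the maximum allowed number of dose reductions will be discontinued from the study", while the synopsis takes them off study treatment only.

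Section 5.8.3 and the synopsis add that a combination patient who has to stop ALRN-6924 counts as off study treatment.

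**Follow-up.** Section 6.13 states: "Patients in Phase 2 will remain on study and be followed for survival and subsequent therapies". The schedules for Cycle 2 and beyond (Appendices D, F, H and J) plan contact about every 2 months after the End of Treatment visit, for survival and later therapy.

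**The concern.** Leaving treatment and leaving the study are different exits. A patient who only stops the drug still contributes survival status. A patient who leaves the study may not. Where the exit is triggered by severe drug toxicity, any loss of survival status is tied to the patient's condition, and Kaplan-Meier estimates assume that censoring is not.

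OS, PFS, and both at 1 year are secondary objectives in the Phase 2a cohorts. Expansion cohorts have about 15–25 patients, so a few lost patients can visibly move a 1-year estimate, and survival status lost at a site may not be recoverable later.

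**Working it through.** **1. The wording side by side.** The entries show what the patient leaves.

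| Cohort and trigger | Synopsis | Body |
|---|---|---|
| PTCL, related non-hematologic Grade 4 | study | study (5.8.2) |
| PTCL, hematologic thresholds | ALRN-6924 | ALRN-6924 (5.8.2) |
| Combination, related Grade 4 | study | study treatment (5.8.1) |
| Combination, persistent events or reductions exhausted | study treatment | study (5.8.1) |
| Combination, any required stop of ALRN-6924 | study treatment | study treatment (5.8.3) |

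Section 6.13 keeps Phase 2 patients on study without a toxicity exception. The first row contradicts it in both places. Rows three and four contradict each other in opposite directions, and row five points to treatment only. Under every wording the drug is stopped, so the disagreement concerns follow-up alone.

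**2. Does it reach an endpoint?** Section 7.6 runs time-to-event endpoints to the event or the end of study. Section 6.13 uses end of study at patient level for Phase 1, where it coincides with the End of Treatment visit. A patient taken off the study could therefore be censored for OS at that point. The supplied SAP covers Phase 1 only, so the Phase 2a censoring rules cannot be checked.

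**3. Possible size (illustration).** The plan has no figure to reproduce. Input from the documents: n = 15–25 per cohort (Section 3.3). Assumed, because the documents give no values:
- q, the share of patients affected: 5%, 10% or 20%;
- S, 1-year OS in the other patients: 30% or 50%;
- S_T, 1-year OS in the affected patients;
- exit from the study soon after the first dose.

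Number affected = n × q: 0.75–1.25 patients at 5%, 1.5–2.5 at 10%, 3–5 at 20%.

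With early censoring the Kaplan-Meier estimate stays near S. The value with full follow-up is (1 − q) × S + q × S_T. The difference is q × (S − S_T), which is largest, at q × S, when S_T = 0:

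| q | S = 30% | S = 50% |
|---|---|---|
| 5% | 1.5 points | 2.5 points |
| 10% | 3 points | 5 points |
| 20% | 6 points | 10 points |

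If S_T is half of S, these values halve. If S_T equals S the difference is zero, and if S_T exceeds S its sign reverses.

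The ceiling q × S belongs to early exit. If the affected patients all live to a later exit, when a fraction S_t of the others is alive, the estimate is S × (1 − q) + q × S / S_t and the ceiling becomes q × S / S_t, which is somewhat larger.

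In counts, with 8 of 20 patients alive at 1 year: 8/20 = 40.0%. With two affected patients who die within the year but are censored early, 8/18 = 44.4%. With three, 8/17 = 47.1%.

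**The case against.** The best answer is that this is loose drafting which no site would act on. Section 4.7 lists unacceptable adverse events as a reason to leave study therapy. Section 5.4.1.1 takes patients with a related Grade 4 hypersensitivity reaction off study treatment. The closing paragraph of 5.8.1 speaks of stopping ALRN-6924. In the schedules the End of Treatment visit also takes place at study withdrawal, and survival contacts follow that visit. This stands to the extent that loss of follow-up is a risk from conflicting instructions, not an exclusion that the protocol states. It does not remove the conflict. Section 8.5 and the schedules name the last dose and study withdrawal as separate events, and 5.8.2 itself uses both terms, so a careful reader may take the contrast as intended.

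Four stronger readings that a reader might infer are not supported:
- *Every Phase 2a patient with a related Grade 4 event is affected.* In PTCL the rule is limited to non-hematologic events with exceptions, and the sentence in 5.8.3 settles much of the combination cohort's position.
- *Adverse event follow-up is cut.* Section 8.5 covers 30 days after the last dose or withdrawal, unless new anticancer therapy starts, and follows related events to resolution, stabilization or new therapy. Section 8.4 keeps related serious events reportable beyond 30 days. All dosed patients stay in the safety population. What remains is that late related events are harder to learn of without contact.
- *Progression data are lost because of this sentence.* No imaging is scheduled after End of Treatment for any patient. That is a separate matter, and new wording here would not change it.
- *The loss can only hide deaths from toxicity.* Deaths are serious adverse events, related ones are reportable at any time, and the direction of bias depends on a prognosis that is not given.

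It is also fair that the effect is modest beside sampling error. For 8/20 the approximate 95% half-width is 1.96 × √(0.4 × 0.6 / 20) = 0.21, or 21 points, and Section 7.1 declares the analyses descriptive. But sampling error is reported with the estimate, and this bias would not be.

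**Conclusion.** The point holds as an internal contradiction. In the PTCL expansion it is explicit, and appears in both the synopsis and the body. In the combination cohort the inherited rules are inconsistent, with 5.8.3 favouring treatment discontinuation only. The consequence is a risk of informative censoring of OS, 1-year OS and the death component of PFS.

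Its size and direction cannot be established from the documents. The figure of 3–5 points at q = 10% assumes that affected patients leave early, are wholly lost to survival contact, and all die within the year. Better survival among them, or continued contact, would shrink or remove it. No view is taken on which events should stop treatment.

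**What to change.** Reconcile the dose-modification text in the synopsis, 5.8.1 and 5.8.2 with 6.13, so that these rules refer to discontinuing study treatment. Add one sentence: Phase 2a patients who stop treatment for toxicity continue the planned survival contacts unless they withdraw consent. The criteria for stopping treatment stay as they are.

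The cost is wording in the next amendment and a memo to sites. No procedure is added, because the two-monthly contacts are already in the schedules.

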5.9 Toxicity, DLT and MTD Evaluation

5.9.1 Toxicity Grading Criteria

Toxicity grading is based on NCI CTCAE v4.03.

5.9.2 Definition of Dose-Limiting Toxicity

A DLT will be defined as any Grade ≥ 3 AE that is considered to be possibly, probably, or definitely related to the study drug, with the following exceptions: (1) for fatigue, nausea, emesis, diarrhea or mucositis, only Grade ≥ 3 AE that do not respond within 48 hours to standard supportive/pharmacological treatment will be considered DLT; (2) for electrolyte imbalances, only Grade ≥ 3 AE that do not respond to correction within 24 hours will be considered DLT; (3) for infusion reactions, only a Grade 3 reaction which caused hospitalization or Grade 4 will be considered a DLT. In addition, specific hematologic DLTs are defined as:

- Thrombocytopenia – Grade 4 of any duration, Grade 3 for ≥ 7 days, or Grade 3 associated with clinically significant bleeding
- Neutropenia – Grade 4 for ≥ 3 days, or any Grade ≥ 3 febrile neutropenia

The above criteria will be used to make individual patient determinations regarding dose reductions, interruptions or discontinuation throughout the course of the trial, but DLTs occurring during Cycle 1 will be used to inform safety and tolerability assessments for dose escalation decisions.

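### Protocol 5.9.2 and 5.8.1 disagree on whether a related, clinically insignificant Grade 3 electrolyte abnormality with no response by 24 hours but resolution within 2 days requires a reduced dose

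*Protocol*

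**What the plan says.** Three statements in the Protocol bear on the same event. Each also appears in the synopsis, under the Phase 1 dose modifications and the DLT definition.

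- **DLT definition (5.9.2).** Among related electrolyte events of Grade 3 or higher, only those "that do not respond to correction within 24 hours will be considered DLT". The rule has no clinical-significance filter. The section then widens its use beyond escalation: "The above criteria will be used to make individual patient determinations regarding dose reductions, interruptions or discontinuation throughout the course of the trial".
- **Consequence of a DLT (5.8.1, closing paragraph).** "A patient who experiences a DLT must continue treatment at a reduced dose level"; the alternative given is to discontinue ALRN-6924 for a related Grade 4 event. The same paragraph bars raising a dose once it has been reduced.
- **Grade 3 rule and its exception (5.8.1).** For a related Grade 3 event, "treatment may be delayed for up to 2 weeks to allow resolution of the toxicity, followed by re-treatment at a reduced dose". Among the exceptions are "clinically insignificant electrolyte abnormalities that resolve within 2 days on optimum treatment".

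Section 5.8.3 applies 5.8.1 to ALRN-6924 dosing in the palbociclib combination cohort.

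**The concern.** The two electrolyte rules differ in three respects. The time limit is 24 hours in one and 2 days in the other. The test is *response* to correction in one and *resolution* in the other. Only the 5.8.1 exception asks whether the abnormality is clinically insignificant. Where the rules overlap, a site can find the event to be a DLT that calls for a lower dose and also an event excepted from dose reduction.

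What is at stake is individual dosing. A reduction cannot be undone, so two patients with the same event could receive different doses for the rest of treatment, depending on which sentence was followed.

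**Working it through.** The plan gives no figure to reproduce, and no sample size, power or error rate is involved. The check is to run a related Grade 3 electrolyte AE through both rules, taking 2 days as 48 hours.

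| Case | Response by 24 h | Clinically significant | Resolved by 48 h | 5.9.2 with the DLT sentence of 5.8.1 | 5.8.1 Grade 3 rule | Conflict |
|---|---|---|---|---|---|---|
| a | Yes | No | Yes, within 24 h | Not a DLT | Excepted | No |
| b | No | No | Yes | DLT, must reduce | Excepted | **Yes** |
| c | No | Yes | Yes | DLT, must reduce | Not excepted | No |
| d | No | Either | No | DLT, must reduce | Not excepted | No |
| e | Yes | No | Yes, between 24 and 48 h | Not a DLT | Excepted | No |

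Only case b conflicts. A Grade 4 electrolyte abnormality that resolves within 2 days does not raise the problem: its exception in 5.8.1 lifts discontinuation but still re-treats at a reduced dose.

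**Can case b occur?** Yes. Sections 8.1.1 and 8.3 count an abnormal laboratory value as an AE if it requires intervention, even when it is not clinically significant. Correction of an electrolyte is an intervention, and 5.9.2 does not ask about clinical significance.

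**Does other text settle it?** No. The 24-hour electrolyte limit recurs in 5.7.3 (intra-patient escalation) and the 2-day limit in 5.8.2 (PTCL dose modifications). For fatigue, nausea, emesis and diarrhea, the DLT exception runs 48 hours. That equals the 2 days of 5.8.1, if the 2-day condition there is read as covering the whole list. Electrolytes are the ones with two lengths, and no passage explains why.

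**Size for an affected patient.** Inputs: 3.1 mg/kg (the DL-6A dose and the combination starting dose); 2.3 mg/kg (the synopsis figure after one 25% step); 2.1 mg/kg (DL-5A in 5.7.2, the level below DL-6A, since 5.8.1 re-treats at the preceding level).

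- 25% step: (3.1 − 2.3) / 3.1 = 0.8 / 3.1 = 0.258, about 26%.
- Preceding level: (3.1 − 2.1) / 3.1 = 1.0 / 3.1 = 0.323, about 32%.

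These are per-infusion dose differences for a patient on 3.1 mg/kg. They show the scale and do not favour either step.

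**The case against.** The strongest reply is that the sentences can be read in order: a general Grade 3 rule, an exception to it, then a specific rule for patients with a DLT that prevails. The exception does not forbid a reduction either, because 5.8.1 allows a discretionary one. The DLT sentence is also softened by "as described above at the discretion of the Investigator" and by the need for the Medical Monitor's agreement, so a site does not act alone.

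Part of this stands. The instructions are *required* against *excepted*, not opposites, and the Medical Monitor's role limits divergence between sites. But the reply does not clearly remove the conflict. The word *must* stays in the sentence, and its reference to what is described above leads back to the section that holds the exception. No text says which rule prevails.

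A reader might infer more than the documents support:

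- **That every electrolyte event settling between 24 and 48 hours is caught.** Cases c and e show otherwise. A clinically significant event is not excepted, and one that responds within 24 hours is not a DLT.
- **That the mismatch changes DLT counts or a cohort step.** Only 5.9.2 defines a DLT, and nothing in 5.8.1 says an excepted event is not one. The event counts the same under either dosing reading. A probability built on an assumed electrolyte event rate would describe all such events, not case b.
- **That the DLT and dose-modification tables would contradict each other.** SAP 8.2 summarises DLTs by category, and SAP 8.1 summarises dose modifications and their reasons. A DLT without a reduction is not an inconsistency between them.
- **That the PTCL cohorts share the same conflict.** Section 5.8.2 does not repeat the sentence requiring a reduced dose after a DLT.

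**Conclusion.** The contradiction is real and narrow. It affects individual dosing for a related, clinically insignificant Grade 3 electrolyte abnormality with no response by 24 hours and resolution within 2 days, in Phase 1 and in ALRN-6924 dosing in the palbociclib cohort. For a patient on 3.1 mg/kg, the choice of reading decides whether a reduction of about 26% to 32% per infusion is applied and then kept. Escalation decisions, DLT counts and the planned tables do not depend on it.

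The documents give no electrolyte event rate, so how often this would arise cannot be stated. The conclusion assumes that *respond* and *resolve* carry their ordinary, different meanings and that 2 days means 48 hours. It is a minor point, worth correcting because the consequence for an affected patient cannot be reversed. No view is taken on which rule is right.

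**What to change.** Reconcile the electrolyte wording in Protocol 5.8.1 (the Grade 3 exception and the DLT sentence) and 5.9.2, and in the matching synopsis paragraphs. The text should settle three things for electrolyte events: the time limit, whether the test is response or resolution, and whether clinical significance matters. Alternatively, keep both rules and add one sentence saying which prevails when a DLT also meets the 5.8.1 exception. The two rules need not share a limit or a verb, provided their relation is stated. The sponsor's clinicians make the choice.

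The cost is a few lines in two sections and the synopsis at the next amendment. Section 5.8.3 picks up the change by reference, and the SAP needs no change.
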